A comprehensive assessment of adherence problems will be firstly conducted to identify the factors that affect adherence, including how and why these factors contribute to poor adherence. Medication-related knowledge and skills will be provided based on individual treatments and barriers to adherence. Motivational interviewing techniques will be used for a better understanding of patients' cognitive factors of adherence behavior. Nurses will discuss with patients to explore their preferences and priorities in medication treatments, setting goals that are practical and acceptable for addressing their problems in medication use, and develop individualized adherence improvement plan to reach these goals. Taking patients' complexity into account, strategies to reduce treatment burden will also be incorporated into intervention sessions, including prioritizing medication and other self-management activities using shared decision making, providing communication skills with healthcare providers and encouraging patients to discuss with the physicians about burdensome regimens, exploring patients' family and social network to support their self-care, and helping them to incorporate self-care activities into daily life. Each face-to-face session will last approximately 30–40 min and will be delivered individually in NCCCR by CNSs. The duration of each session can be adjusted by CNSs in accordance with the patients' barriers and problems to medication adherence. The three face-to-face sessions are designed to complete at 7–10-day intervals over 4 weeks. Before the first face-to-face session, nurses will review patients' clinical health records to confirm the screening criteria.

Patients will be asked to bring all medications to HMC. After the conclusion of the last face-to-face session, education materials containing instructions and information on the name, purpose, side effects, and special tips for each usual chronic medication and medication skills will be provided to participants. After the face-to-face sessions, patients are followed up by two weekly by telephone. Each telephone encounter lasted 10–20 min. The aim, content, and delivery strategy of each session are shown in Table 1.

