
2nd face-to-face education session
 
 To help patients change negative attitudes and beliefs about medication treatments and become motivated to it. 	
(1) Give patients the opportunity to understand the importance of medication adherence and the consequences of non-adherence.
 
(2) Encourage patients to express feelings and barriers to family members and seek assistance, where appropriate. (3) Provide a list of local resource information to patients (e.g., medical care institutions, psychological support organizations, and peer support teams).
	
 ❖ Motivational interviewing

3rd face-to-face education session
 
 To help patients develop skills and strategies to overcome practical barriers of their medication treatments. To help patients set goals and develop a workable adherence improvement plan. 	
(1) Nurses will educate patients about six skills in medication self-management:
 
 Identifying and coping with medication side effects; Incorporating medication treatments into daily life; Obtaining and updating medication adherence-related information; Acquiring, self-cueing and self-administering medications; Effectively communicating with healthcare providers; Acquiring social and instrumental support for adherence. 
(2) Ask patients to select three skills they most want to learn or help most to take their medications; Discuss with patients
	
 ❖ Planning coping responses ❖ Goal setting

about strategies on how to apply the three skills to their self-management.

(3) Set goals and help make an individualized adherence improvement plan based on patients' expectations and preferences.

(1) Ask whether patients can adhere to the medications in the last week and if not, the reasons for medication non-adherence will be asked and discussed with patients.

2-week Telephone follow-

- To further explore the challenges and difficulties in medication self-management.
- To provide feedback and suggestions according to patients' performance.

(2) Ask whether patients can apply skills in medication self-management and encounter any challenges and concerns in medication-taking.

(3) Further adherence education where needed.

(4) Conclude what is discussed and encourage patients to contact healthcare providers when they have adherence problems

- ❖ Active listening

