Based on screening & randomization tool

Risk

In this section describe the anticipated risks associated with participation in the research (i.e. illness, injury, death)

No risk is anticipated as part of study

Bio-Specimens & Sample Collection

In this section describe what specimens or samples will be collected specifically for research, if specimens will be stored long-term and/or destroyed. Consider what happens to data/specimens if subject withdraws consent

NA

Outcomes

In this section provide details on the outcome measures and the anticipated primary & secondary outcomes

Outcome assessment

The nurses masked to the participant allocation will collect follow-up data through telephone interview. Participants will be assessed at baseline (T0), in the week immediately post-intervention (7th week) (T1), and at 3-month post-intervention (T2). Table 2 provides an overview of primary and secondary outcomes as well as covariates at each time point. Permission will be obtained from the original authors to use the scales for this study.

Primary outcome

Medication Adherence

The English version of Morisky-8 will be administered to assess medication adherence of the participants(29). The Morisky-8 is a self-reporting measure of unintentional and intentional medication non-adherent behaviors with a yes and no response. The total score of the moresky-8 ranges from 0 to 8, with a higher score representing higher adherence to medication.

Table 2 Schedule of enrolment, interventions, and assessments

TIMEPOINT	STUDY PERIOD				
	Enrolment	Baseline T0	Intervention	Follow-up	
				T1	T2
ENROLMENT					
Eligibility screen	X				
Informed consent	X				
Allocation		X			
INTERVENTION					
Intervention group			X		
Control group			X		
ASSESSMENTS					
Primary outcome					
Medication adherence (Moresky-8)		X		X	X
Secondary outcomes					
Medication knowledge (PKMUQ)		X		X	X
Medication beliefs (BMQ)		X		X	X
Medication self-efficacy (SEAMS)		X		X	X
Treatment burden (TBQ)		X		X	X
Potential covariates					

Socio-demographics questionnaire)	(Patients	X
Number of prescribed medications (one-item question)		X
Depressive symptoms (PHQ-9)		X

Secondary

outcomes

Medication Knowledge

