The treatment burden will be measured by the 10-item Multi-morbidity Treatment Burden Questionnaire (MTBQ)(36). It assesses the wide range of behavioral and emotional burdens involved in treatment implementation and treatments associated with taking multiple medicines, self-monitoring their health and making lifestyle changes. Each item is scored on 6-point Likert scale, ranging from 0 = does not apply to 5 = most difficult. Scores are summed to derive a total score ranging from 0 to 50 with a higher score indicating a higher level of treatment burden.

Potential covariates

Socio-demographic characteristics and the number of prescribed medications

Socio-demographic characteristics will be collected at baseline from patients. Patients will be asked about age, gender, educational level, marital status, monthly income, and the number of prescribed medications.

Intervention fidelity and contamination

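### The treatment-burden total scores 'does not apply' as the bottom step of a difficulty scale, so it partly counts how many tasks apply, and the between-arm comparison can be distorted in an unknown direction

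*Combined protocol and SAP*

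**What the plan says.** Section 7, under Outcomes, Treatment burden, names the "10-item Multi-morbidity Treatment Burden Questionnaire (MTBQ") and gives the item rule: "Each item is scored on 6-point Likert scale, ranging from 0 = does not apply to 5 = most difficult". The total follows: "Scores are summed to derive a total score ranging from 0 to 50 with a higher score indicating a higher level of treatment burden". The only subject matter given for the items is "taking multiple medicines, self-monitoring their health and making lifestyle changes". Codes 1 to 4 carry no labels, no item is printed, and the list in Section 14 (Appendices) does not include this questionnaire. No passage excludes, rescales or averages over items that do not apply.

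Treatment burden is one of the secondary objectives in Section 4 and a determinant of adherence in the extended model described under Theoretical framework. Section 8 compares changes in the repeated outcomes between arms by generalized estimating equations, adjusted for baseline variables.

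The Intervention group text in Section 6 says that the sessions include burden-reducing strategies, among them prioritising activities and "providing communication skills with healthcare providers and encouraging patients to discuss with the physicians about burdensome regimens". Table 1 lists skills taught in the third session, such as "Obtaining and updating medication adherence-related information".

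**The concern.** A response meaning that a task is not part of the patient's treatment is placed one step below the easiest rating of a task that is. The sum then treats the move from not applicable to applicable and easy as one more unit of burden, equal in weight to any other one-step rise in difficulty. Two patients with the same experience of difficulty can get different totals only because their treatments involve different numbers of tasks.

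Between patients at baseline, randomisation balances this on average. The difficulty arises after randomisation. The programme tries to change how patients manage their treatment, so it may change which tasks apply. Such a change would enter the between-arm difference as if it were a change in burden. Adjustment for baseline variables does not remove a shift that happens later. A true change in burden could be hidden, or an apparent one produced, in an outcome that the protocol uses to explain how the programme works.

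**Working it through.** **Inputs.** From the Treatment burden text: 10 items, codes 0 to 5, 0 = does not apply, 5 = most difficult, summed. From the Sample size text: 47 evaluable participants per arm. Assumed, because the documents give no figure: code 1 = not difficult; a standard deviation of 5, 8 or 10 points for the total; and *k*, the between-arm difference in the mean number of applicable items that arises after randomisation.

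**1. Reproduce the stated range.** 10 × 0 = 0 and 10 × 5 = 50. This matches the protocol, so 'does not apply' enters the sum as a real zero and is not set aside as missing.

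**2. What the total contains.** Let *m* be the number of applicable items and *x* the code of each (1 to 5). Then

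total = *m* + Σ(*x* − 1), summed over the applicable items.

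The first term counts tasks. The second measures difficulty above the lowest applicable level. Check at the maximum: *m* = 10 with every *x* = 5 gives 10 + 40 = 50. This step uses only the fact that 0 is reserved for 'does not apply'.

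**3. Size between patients, if code 1 means 'not difficult'.** The second term is then zero for anyone without difficulty, and the total equals *m*.
- All ten tasks apply, all easy: 10 × 1 = 10.
- Two tasks apply, both easy: 2 × 1 = 2.
- The gap is 8 points with no difference in difficulty. The possible spread is 0 to 10, and 10/50 = 20% of the range.

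**4. Size between arms, illustration only.** If the arms differ by *k* in mean applicable items, and those extra items are rated at the lowest level, the mean difference moves by *k* points. The standardised shift is *d* = *k*/SD. If there is no true difference in burden, the chance that this shift alone gives p < 0.05 in its own direction is approximately Φ(*d*/√(2/47) − 1.96) for a simple two-group comparison.

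| *k* | SD 5 | SD 8 | SD 10 |
|---|---|---|---|
| 1 | *d* = 0.20, 16% | *d* = 0.125, 9% | *d* = 0.10, 7% |
| 2 | *d* = 0.40, 49% | *d* = 0.25, 23% | *d* = 0.20, 16% |

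The table applies equally to positive and negative *k*. Nothing in the documents says which values of *k* or SD are realistic.

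**5. After recoding.** With 'does not apply' = 0 and codes 1 to 5 mapped to 0 to 4, the total is Σ(*x* − 1), with range 0 to 10 × 4 = 40. Both patients in step 3 score 0. The stated 0–50 sum equals the recoded total plus *m*, so reporting all three quantities shows exactly where any difference comes from.

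**The case against.** The strongest reply is that no between-arm shift has been shown. No questionnaire item is printed, so it cannot be confirmed that talking to physicians, seeking support or updating information is a scored task. The areas that are named probably apply to many participants at entry, since eligibility requires at least two comorbidities, a chronic medication for at least three months and independent management of medicines. Under Control group, both arms receive physician consultation, education and regimen discussion. Table 1 asks patients to choose only three of the six skills. All of this stands, and it is why no size can be given for *k*.

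A reader might go further and infer that the score is biased against the intervention, because the sessions encourage new activities such as "encouraging patients to discuss with the physicians about burdensome regimens". The documents do not support that reading. The same paragraph describes prioritising medication and other self-management activities, which could make tasks stop applying and lower the score artificially.

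Two further objections have force. Codes 1 to 4 are unlabelled: if 1 already means slight difficulty, that point is real burden and recoding it to 0 would erase it. The protocol would then have no code for a task that applies without difficulty, which is also something to settle. And more tasks can fairly be called more workload. But the scale is anchored at the top by difficulty, and the protocol does not say that task count is meant to contribute.

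None of this changes step 2 of the working: the rule as written mixes count and difficulty.

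**Conclusion.** The point holds as a defect in the scoring rule of one secondary outcome. As written, the total is the number of applicable tasks plus the difficulty above the lowest applicable level, and this follows from the protocol's own codes. If code 1 means 'not difficult', patients without any difficulty can differ by up to 10 of 50 points.

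That the sessions alter which tasks apply is a reasonable inference from their content, not a stated fact. The resulting distortion between arms could run either way, and its amount is unknown; the figures in step 4 of the working show only what assumed shifts would do. The primary outcome and the sample size are not touched. The rule should be corrected because following it as written can mislead and the correction is cheap.

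**What to change.** Before outcome data are unblinded:

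1. Confirm all response labels against the instrument and print them in the protocol. Record 'does not apply' as its own response, distinct from every difficulty level, including in the telephone interviews used for follow-up.
2. If the lowest applicable level means 'not difficult', score it and 'does not apply' both as 0 and the remaining levels 1 to 4. Replace the 0–50 range with 0–40. If the lowest level means some difficulty, this recode should not be used, and the protocol must say how a task that applies without difficulty is scored.
3. Report the stated 0–50 sum and the number of applicable items, by arm and time point, as supporting analyses.

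A mean over applicable items is not a good substitute: it conditions on a state that arises after randomisation, and it is undefined for a patient with no applicable item.

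The cost is a label check, one recode and an amended range; no extra data are needed. A small downside is that the recoded total no longer separates 'not difficult' from 'does not apply', though the raw responses keep the distinction. The same amendment can align the label in Table 2, "Treatment burden (TBQ"), with the abbreviation in the text. That is clerical and carries no weight here.

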HMC RESEARCH PROTOCOL

Nurse-led medication self-management intervention in the improvement of medication adherence in adult patients with multi-morbidity: A Feasibility Randomized controlled trial

[name]

[name]

Date-2 Nov 2022

NCT- Not available

1. Summary

Back ground & Aims

Adult patients suffering from multimorbidity are at high risk of medication non-adherence. It has been well established that self-management support is an effective strategy to enhance medication adherence for patients with chronic conditions. However, little is known about the effect of the medication self-management intervention in Adult patients with multimorbidity. The aim of this study to evaluate the effectiveness of a nurse-led medication self-management intervention in improving medication adherence and health outcomes in adult patients with multimorbidity.

Methods

This study is a single centre, single-blind, two-arm randomised controlled trial. Adult patients with multi-morbidity will be recruited from NCCCR Qatar. A total of 100 participants will be randomly allocated to receive standard care or standard care plus the medication self-management intervention. The intervention will be delivered by clinical nurse specialists. The 6-week intervention includes three face-to-face education sessions (2st week, 4rd week and 6th week) and two weekly (8th week and 10 week) follow-up phone calls. Participants in the control group continue to receive all respects of standard care offered by healthcare providers, including chronic disease management, drug prescription, referral to hospital specialists, health education and consultations regarding patients' diseases and treatments during centre visits.

Outcome

The primary outcome is medication adherence as measured by the 5-item Medication Adherence Report Scale. Secondary outcomes include medication self-management capacity (medication knowledge, medication beliefs, and medication self-efficacy), treatment experiences (medication treatment satisfaction and treatment burden). All outcomes will be measured at baseline, immediately post-intervention (7th week), and at 3-month post-intervention.

2. Abbreviations and Acronyms

NCCCR- National Cancer Care Center and Research

CNS- Clinical Nurse Specialist

IMB- Information-Motivation-Behavioral Skills

3. Introduction / Background

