Control group Participants in the control group will continue to receive standard care from Physicians, nurses, and clinical pharmacists in the NCCCR. Physicians are the primary providers and coordinators of care for patients with chronic conditions. Physicians provide patients consultations and education regarding their diseases and treatments (typically clinician-centred) at each patient visit to the chronic disease clinic. Referral to hospital specialists will be made by physicians as needed. For patients diagnosed with hypertension and/or diabetes, Physicians are required to provide scheduled follow-up via telephone contact. CNSs assist physicians with chronic disease management. In respect of medication management, Physicians will prescribe medication regimens, provide medication consultations (including instructions on the medications' dosage, methods, and frequency), and adjust regimens where appropriate through discussion with patients. No structural medication self-management education session will be provided for patients in standard care group.

Table 1 The Nurse-led Medication Self-Management Intervention Sessions

Aim	Content	Delivery strategy

1st face-to-face education session
 
 To identify patients' problems and barriers to medication adherence. To educate patients on the right information about medication taking and adherence. 	
(1) Inform patients about the purpose and procedure of the whole intervention.
 
(2) A structured patient-centered adherence assessment, covering a checklist with all the questions about patients' medication experiences, including effectiveness and side effects of the drugs, treatment burden, and barriers to adhering to medications.
 
(3) Educate patients on disease- and medication-related information and correct misinformation, including the name, dosage, frequency, timing, purpose of each medication, potential side effects, and special administration considerations.
 
(4) Encourage patients to ask questions and ensure that they understand what is said to them.
	
 ❖ Individualization ❖ Teach-back technique

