The principal investigator will be responsible for monitoring the procedure of the whole study. The intervention logbook will be used by participating nurses to record the number, duration, and administration date of face-to-face sessions and follow-up phone call sessions. To ensure that the delivery of motivational interviewing is consistent with its principals, all motivational interviewing sessions will be audiotaped if permitted by the participant. A random 20% sample will be reviewed using Motivational Interviewing Treatment Integrity Coding Manual 4.2.1 (37) by the local motivational interviewing nurse expert throughout the duration of the intervention. The principal investigator will meet with intervention nurses to discuss the experiences and difficulties to deliver the intervention sessions and provide feedback weekly. Intervention logbooks will also be examined weekly by the principal investigator and further training for nurses will be considered if the delivery of the intervention is not per protocol. Contamination may occur whereby control group participants also receive usual nursing care or interact with intervention group participants. However, the current study is expected to be at a low risk of contamination because (1) patients with chronic diseases predominately receive medication management by physicians, the involvement of nurses in medication treatment and consultation is rare, (2) the multifaceted interventions with individualized cognitive behavior component cannot easily be transferred from one participant to another. Also, the following strategies will be introduced to minimize contamination. First, participants and nurses will be provided with clear information on the nature and purpose of the study. Second, Nurse/researchers will ask participants keep the education materials to themselves until the end of the study. Finally, only intervention nurses will receive training to deliver the intervention and they will be requested not to discuss the intervention with their colleagues who might be involved in the control group. At the end of the trial, participants in the control arm will be asked whether they have received any information or education on their medications, causal average effect analysis will be considered if high degree contamination occurs (38).

Data Collection, Management & Confidentiality

a) *Indicate below HOW study data will be collected for the proposed research.*

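### The contamination question put to controls cannot tell standard-care education from exposure to the intervention, so it overstates contamination

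*Combined protocol and SAP*

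**What the plan says.** The section on intervention fidelity and contamination describes one end-of-trial check, for the control arm only: "participants in the control arm will be asked whether they have received any information or education on their medications". As described, the question has no limit on provider, content or source. The same sentence adds that "causal average effect analysis will be considered if high degree contamination occurs". No threshold for a high degree, exposure variable or estimator is given there, and Section 8 does not mention this analysis.

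The section describes contamination this way: "Contamination may occur whereby control group participants also receive usual nursing care or interact with intervention group participants".

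The Control group text sets out what controls are meant to receive: "Physicians provide patients consultations and education regarding their diseases and treatments (typically clinician-centred) at each patient visit to the chronic disease clinic". Physicians also advise on how much of each medicine to take, how and how often. The Summary likewise counts as standard care "health education and consultations regarding patients' diseases and treatments during centre visits". What controls do not receive is stated separately: "No structural medication self-management education session will be provided for patients in standard care group".

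**The concern.** A contamination measure should pick up what leaked from one arm to the other. This one asks about something the protocol gives to both arms. A yes may mean only that the control patient attended clinic and was told how to take a medicine.

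Two things are at stake. First, the contamination rate would not be interpretable. In a trial titled as a feasibility study, that rate is something a later trial would want, and it would be needed to test the protocol's own expectation that contamination risk is low. Second, the answer is the only stated basis for deciding whether to run the causal analysis. If it were also used there as treatment receipt, the exposure difference between arms would look smaller than it is and the estimated effect larger.

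**Working it through.** **Step 1: the texts side by side.**

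- Asked of controls: any medication information or education (Intervention fidelity and contamination).
- Given to controls as standard care: education on disease and treatment at chronic disease clinic visits, and medication consultations (Control group; Summary).
- Withheld from controls: the structured self-management sessions (Control group). The item does not ask about these.
- Content overlap: the first session in Table 1 covers dosage and frequency, which the physicians' consultations also cover.
- Staff overlap: "CNSs assist physicians with chronic disease management" (Control group), and the nurses who deliver the intervention must do chronic disease management in their routine work (Recruitment).

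A control advised by a physician and a control given an intervention session would both answer yes. The description of contamination adds to the confusion by counting usual nursing care, which is itself part of the control condition.

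**Step 2: effect on a causal estimate, as an illustration.** The plan has no figure to reproduce. I assume the usual Wald form:

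estimate = ITT effect / (share treated in the intervention arm - share of controls counted as treated)

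*No true contamination, full uptake.* With p the share of controls answering yes, the inflation factor is 1/(1 - p):

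- p = 25%: 1/0.75 = 1.33
- p = 50%: 1/0.50 = 2
- p = 75%: 1/0.25 = 4
- p = 90%: 1/0.10 = 10
- p = 100%: zero denominator, no estimate

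*5% true contamination, full uptake, true effect 0.52 SD.* The 0.52 is the sample-size section's effect size; the 5% is assumed. The ITT effect is 0.52 × 0.95 = 0.494. If a share f of uncontaminated controls answer yes because of standard care, the observed yes rate is 0.05 + 0.95f:

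- f = 0: yes rate 5%; 0.494/0.95 = 0.52, the true value
- f = 0.3: yes rate 33.5%; 0.494/0.665 = 0.74
- f = 0.5: yes rate 52.5%; 0.494/0.475 = 1.04
- f = 0.8: yes rate 81%; 0.494/0.19 = 2.6
- f = 1: yes rate 100%; undefined

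If uptake were 90% and more than 90% of controls answered yes, the denominator would be negative and the estimate would change sign.

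**Step 3: precision.** At the 47 per arm in the sample-size section, the standard error of a standardised difference is about √(2/47) = 0.21. With the denominator treated as fixed, it is divided by the same quantity as the estimate: at a denominator of 0.1 it is about 2.06. The ratio of estimate to standard error does not change.

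**Step 4: the primary analysis.** Section 8 analyses all randomised patients by allocation with GEE models. The contamination item does not enter them.

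**The case against.** The strongest reply is that little depends on this item. The causal analysis is optional, Section 8 omits it, and the primary analysis ignores the item. That stands, and it limits the point to a supplementary measure and analysis.

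Several stronger readings are tempting, but the documents do not support them.

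- *Every control will answer yes.* The documents do not say so. Answers depend on clinic attendance and recall, and the question's exact wording is not given: the section describes it in running text, and the appendix list names no contamination form. The final wording might restrict it to education beyond usual care.
- *High contamination will nearly always be found.* This cannot be derived, because a high degree is not defined.
- *The planned causal analysis is wrong.* It is only to be considered, with no named estimator or exposure variable. Bias follows only if these answers serve as treatment receipt.
- *Real leakage would go undetected.* A control given an intervention session would also answer yes. The case is mixed in with usual care, not missed: the fault is poor specificity, not poor sensitivity. The protocol also says that nurses are rarely involved in medication consultation.
- *A spurious significant result would follow.* Estimate and standard error grow by about the same factor, so the inflation affects the size of the effect and not the strength of evidence against no effect.

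The item as described still asks about care that controls are meant to receive, and nothing elsewhere in the protocol corrects that.

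**Conclusion.** The concern holds as a measurement fault. The item does not separate standard care from intervention exposure, so it overstates contamination and gives a rate that cannot be interpreted. This rests on the protocol's own text and needs no assumption beyond the item being asked as described.

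The consequences are conditional. The item could falsely trigger the causal analysis. If its answers were used as treatment receipt, the estimate would be inflated by 1/(1 - p), or not exist at p = 100%. That figure assumes a Wald estimator, full uptake in the intervention arm and no true contamination, and the values of p are illustrative. The intention-to-treat result is not at risk. The change is worth making because it is cheap and because a non-specific yes cannot be reclassified later.

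**What to change.** Before end-of-trial questioning starts, replace the item. After the T2 scales are complete, ask controls only about exposure specific to the intervention:

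- a structured medication self-management session or study follow-up call of the kind in Table 1, worded to exclude routine CNS contact;
- motivational interviewing, or a written individual adherence improvement plan;
- the trial's education materials.

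Define contamination as yes to any of these, and delete usual nursing care from the description of contamination. Use only this variable as control-arm exposure in any causal analysis, and take intervention-arm receipt from the existing logbooks. If the causal analysis is kept, state in Section 8 what counts as a high degree and which estimator will be used.

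The cost is one or two extra questions per control participant and a short protocol edit. Asking after the T2 scales keeps the new questions from influencing the outcome answers.
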